6.2.1 Management of Infections

Everolimus has immunosuppressive properties and may predispose patients to bacterial, fungal, viral or protozoal infections, including infections with opportunistic pathogens. Localized and systemic infections, including pneumonia, other bacterial infections, invasive fungal infections, such as aspergillosis or candidiasis and viral infections including reactivation of hepatitis B virus, have been described in patients taking everolimus. Some of these infections have been severe (e.g. leading to sepsis, respiratory or hepatic failure) and occasionally have had a fatal outcome.

Physicians and patients should be aware of the increased risk of infection with everolimus and treat pre-existing infections prior to starting treatment with everolimus. While the patient is taking everolimus, the treating investigator should be vigilant for symptoms and signs of infection; if a diagnosis of infection is made, institute appropriate treatment promptly and consider interruption or discontinuation of everolimus.

If a diagnosis of invasive systemic fungal infection is made, discontinue everolimus and treat with appropriate antifungal therapy.

Cases of pneumocystis jirovecii pneumonia (PJP), some with a fatal outcome, have been reported in patients who received everolimus. PJP may be associated with concomitant use of

CONFIDENTIAL

STUDY DRUG(S): EVEROLIMUS
FINAL PROTOCOL DATE: 19 JUNE 2014

SCRI INNOVATIONS STUDY NUMBER: BRE 212
VERSION 1.0

corticosteroids or other immunosuppressive agents. Prophylaxis for PJP should be considered when concomitant use of corticosteroids or other immunosuppressive agents are required.

6.2.2 Management of Skin Toxicity

For patients with Grade 1 toxicity, no specific supportive care is usually needed or indicated. Rash must be reported as an AE. Patients with Grade 2 or higher toxicity may be treated with the following suggested supportive measures at the discretion of the investigator: oral minocycline, topical tetracycline, topical clindamycin, topical silver sulfadiazine, diphenhydramine, oral prednisolone (short course), topical corticosteroids, or pimecrolimus.

6.2.3 Management of Hypersensitivity reactions

Hypersensitivity reactions manifested by symptoms including, but not limited to, anaphylaxis, dyspnea, flushing, chest pain or angioedema (e.g. swelling of the airways or tongue, with or without respiratory impairment) have been observed with everolimus. Please refer to Table 4 for management of non-hematologic toxicities related to everolimus.

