6.2 Everolimus Dose Modifications Due to Non-Hematologic Toxicity

Dose reductions and management of non-hematologic toxicities related to everolimus are defined in Table 3 and Table 4.

CONFIDENTIAL

STUDY DRUG(S): EVEROLIMUS
FINAL PROTOCOL DATE: 19 JUNE 2014

SCRI INNOVATIONS STUDY NUMBER: BRE 212
VERSION 1.0

Table 3 Everolimus Dose Modifications and Management of Hepatic Toxicity

Toxicity	Actions
AST or ALT elevation Grade 3 (> 5.0 - 20.0 ULN)*	Interrupt everolimus administration until resolution to \leq Grade 1 (or \leq Grade 2, if baseline values were within the range of Grade 2). If resolution occurs \leq 7 days, reintroduce everolimus at the dose level prior to interruption. If resolution occurs > 7 days, or if event recurs within 28 days, hold everolimus until recovery to \leq Grade 1 or baseline value and reintroduce everolimus at one dose level lower, if available.
AST or ALT elevation Grade 4 (> 20 x ULN)*	Interrupt everolimus administration until resolution to \leq Grade 1 (or \leq Grade 2, if baseline values were within the range of Grade 2). If resolution occurs \leq 7 days, reintroduce everolimus at one dose level lower. If resolution occurs > 7 days, discontinue everolimus.
Recurrence of Grade 4 after dose reduction or toxicity requiring Everolimus interruption for > 28 days	Discontinue everolimus.
Grade 3 or 4 clinical liver failure (asterixis or encephalopathy/coma)	Discontinue everolimus.

* Should HCV flare be confirmed, the guidelines for flare must take precedence (See Section 6.2.10).

CONFIDENTIAL

STUDY DRUG(S): EVEROLIMUS
FINAL PROTOCOL DATE: 19 JUNE 2014

SCRI INNOVATIONS STUDY NUMBER: BRE 212
VERSION 1.0

Table 4 Everolimus Dose Modifications and Management of Non-Hematologic Toxicity

Toxicity	Actions
Intolerable Grade 2 mucositis, or Grade 3 AE (except pneumonitis [see Table 5] and except hyperglycemia or hypercholesterolemia [See Section 6.2.5])	Interrupt everolimus administration until resolution to \leq Grade 1 or baseline value. If resolution occurs within \leq 7 days, reintroduce everolimus at the dose level prior to interruption. If resolution occurs $>$ 7 days, or if event recurs within 28 days, hold everolimus until recovery to \leq Grade 1 or baseline value and reintroduce everolimus at one dose level lower, if available. Patients will be withdrawn from the study if they fail to recover to \leq Grade 1 or baseline value within 28 days.

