Recurrence of Grade 2 mucositis or Grade 3 AE after dose reduction	Reduce dose to the next lower dose level, if available. The lowest possible dose level of everolimus is 5 mg every other day (2.5 mg daily). Below this level, everolimus must be discontinued. If toxicity recurs at Grade 3, consider discontinuation.
Grade 4 AE	Hold everolimus until recovery to \leq Grade 1 or baseline value. Reintroduce everolimus at one dose level lower, if available.
Grade 4 AE recurrence after dose reduction	Discontinue everolimus.
Any non-hematologic toxicity requiring interruption for $>$28 days.	Discontinue everolimus.

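### After anaphylaxis or life-threatening hypersensitivity, Section 6.2.3 points only to Table 4, whose default is to restart everolimus; no specific rule requires a stop before the first re-challenge

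*Protocol*

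**What the plan says.** Protocol Section 6.2.3 names anaphylaxis and angioedema of the airways or tongue among the hypersensitivity reactions that "have been observed with everolimus. Please refer to Table 4 for management of non-hematologic toxicities related to everolimus". It gives no other instruction. Section 6.2.4, on angioedema with ACE inhibitors, states a raised risk and prescribes no action.

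Table 4 (Section 6.2) works by grade, not by type of reaction:

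- **Grade 3.** The row covers any "Grade 3 AE (except pneumonitis [see Table 5] and except hyperglycemia or hypercholesterolemia". Everolimus is interrupted until Grade 1 or less or baseline. If that takes 7 days or less, the action is to "reintroduce everolimus at the dose level prior to interruption". If it takes longer, or the event recurs within 28 days, the restart is one level lower.
- **Grade 4.** No exceptions are named. After a hold until recovery, the action is "Reintroduce everolimus at one dose level lower, if available".
- **Limits.** Everolimus stops on "Grade 4 AE recurrence after dose reduction" and for "Any non-hematologic toxicity requiring interruption for" more than 28 days. At the lowest dose level, "Below this level, everolimus must be discontinued". For a repeated Grade 3 event the wording is softer: "If toxicity recurs at Grade 3, consider discontinuation".

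Three other places allow a stop. Section 3.3 lists intolerable toxicity as a reason for discontinuation, Section 5 ends treatment for toxicity that requires it, and Section 7.5 recognises a decision by the study physician. The SAP's efficacy assessment timepoints repeat the Section 7.5 wording; the SAP has no rule of its own on this point.

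**The concern.** A generic toxicity table asks how severe the event was and how fast it cleared. For most toxicities that is a reasonable guide to whether the patient can tolerate the drug again. For anaphylaxis, fast recovery is a poor guide, because the question is what happens on the next exposure. Yet in Table 4 fast recovery is what leads to the least cautious branch, a restart at full dose.

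The protocol also treats hypersensitivity differently before and after entry. Exclusion criterion 1 bars a patient with known hypersensitivity to any mTOR inhibitor. A patient who first shows it on study has, as the written default, a restart. Everolimus is self-administered by outpatients (Sections 5.1.1 and 8.1.2), and neither 6.2.3 nor Table 4 asks for an observed first dose at re-challenge.

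What is at stake is the safety of individual patients: a repeat exposure after a life-threatening reaction.

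**Working it through.** No power or sample-size figure is involved. The check traces a first hypersensitivity reaction through the written rules and asks whether anything requires a stop before re-challenge.

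**Dose levels (Table 1).** Start 10 mg daily; level -1, 5 mg daily; level -2, 5 mg every other day.

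**First re-challenge dose for a patient on 10 mg daily, as a share of the prior dose:**

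| First event | Rule | Restart dose | Share |
|---|---|---|---|
| Grade 3 hypersensitivity, resolved in 7 days or less | Table 4 | 10 mg daily | 10/10 = 100% |
| Grade 3 hypersensitivity, resolved after more than 7 and up to 28 days | Table 4 | 5 mg daily | 5/10 = 50% |
| Grade 4 hypersensitivity, resolved within 28 days | Table 4 | 5 mg daily | 5/10 = 50% |
| Grade 3 pneumonitis | 6.2.9, Table 5 | about 5 mg daily, if restarted | about 50% |
| Grade 4 pneumonitis | 6.2.9, Table 5 | none | 0% |

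**Do Table 4's limits act before the first re-challenge?**

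1. Grade 4 recurrence after dose reduction: no. It presupposes a re-challenge.
2. Grade 3 recurrence: no. It also comes after re-exposure, and it asks only for consideration.
3. Interruption over 28 days: it can, but it depends on duration and not on the type of reaction. I assume that most acute reactions clear well within 28 days; the documents give no figure.
4. Lowest dose level: only after a Grade 4 event, or a Grade 3 event that is slow to resolve, in a patient already on 5 mg every other day.

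**Where does the protocol leave its restart default?** It stops everolimus at the first event for Grade 4 pneumonitis (6.2.9, Table 5), Grade 3 or 4 clinical liver failure (Table 3), invasive systemic fungal infection (6.2.1) and hepatitis C flare (Table 8). Hypersensitivity has no such rule.

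**Stomatitis is not a clean comparator.** Section 6.2.6 gives a lower dose after Grade 3 and a stop after Grade 4. Table 4 does not except stomatitis, so read alone it would restart Grade 3 stomatitis that resolves within 7 days at 10 mg, and Grade 4 at 5 mg. The two places conflict, and the contrast with hypersensitivity holds only if 6.2.6 prevails. Pneumonitis is the firmer comparator, because Table 4's Grade 3 row itself sends the reader to Table 5.

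**The case against.** The strongest reply is that no one is forced to re-challenge. Section 3.3 requires discontinuation once toxicity is judged intolerable, Section 5 allows for toxicity that requires cessation, and Section 7.5 presupposes that the study physician may stop. This stands. A reader might infer from Table 4 that the protocol compels a restart after anaphylaxis, and the documents do not support that reading. What remains is that each exit rests on judgement. Section 3.3 does not say whether a reaction that has resolved still counts as intolerable, so about nine sites could answer differently, while Table 4 gives them an explicit instruction to restart.

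A second reply is that restarting is the protocol's general default. Renal failure, described as sometimes fatal, has the same pointer to Table 4 (6.2.5). First Grade 4 hematologic events restart one level lower (Table 2), as does Grade 4 AST or ALT elevation that resolves within 7 days (Table 3). This also stands: hypersensitivity has not been singled out for laxer handling. But a general default is not thereby suited to anaphylaxis, and the protocol does depart from it for other named conditions.

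Third, Section 8.1.3 places precautions in the Investigator's Brochure, which is not among the documents and may be stricter. That cannot be checked here. Section 6.2.3 does not send the investigator there for management, and a stricter Brochure would leave the two in conflict.

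Finally, no text in the protocol says that re-challenge after an on-study reaction is inappropriate. The case for a mandatory stop rests on clinical judgement, supported by exclusion criterion 1 and the Grade 4 pneumonitis rule.

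**Conclusion.** The point holds in a limited form. For anaphylaxis and airway angioedema the written default is a restart after recovery: at 100% of the prior dose after a first Grade 3 event that resolves within 7 days, and at 50% (5 mg from 10 mg) after a first Grade 4 event. No hypersensitivity-specific rule requires a stop before that re-challenge. A stop is permitted, but it is not mandatory for the reaction itself.

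Two further readings are not supported. One is a count of patients put at risk: the documents give no incidence of hypersensitivity. The other is an effect on the trial's statistics: the sample size and the primary analysis are unaffected.

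The conclusion assumes that the Investigator's Brochure does not already impose a stop, and that acute reactions usually resolve inside the 28-day limit. The gap should be fixed because the potential harm is severe and the correction is small.

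**What to change.** - In Section 6.2.3, state that everolimus is permanently discontinued after anaphylaxis of any grade, or any Grade 4 hypersensitivity reaction including life-threatening airway angioedema, when attributed to everolimus.
- In Table 4, add to both the Grade 3 and the Grade 4 rows: *except anaphylaxis and Grade 4 hypersensitivity, see 6.2.3*.
- Leave other Grade 3 hypersensitivity reactions under Table 4's existing hold rule unless the sponsor's clinicians set a stricter one. Removing them without a replacement would leave no hold instruction at all.
- For angioedema in a patient taking an ACE inhibitor (6.2.4), assess causality first. A blanket stop could wrongly attribute the event to everolimus.
- Check the wording against the Investigator's Brochure.

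The cost is a clarifying amendment with no new procedures. The downside is that a few patients who could have tolerated re-challenge will stop everolimus. Under Section 6 they should continue anti-estrogen therapy if they are deriving clinical benefit.

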6.2.4 Angioedema with concomitant use of angiotensin-converting enzyme (ACE) inhibitors

Patients taking concomitant ACE inhibitor therapy may be at increased risk for angioedema (e.g. swelling of the airways or tongue, with or without respiratory impairment).

6.2.5 Renal Failure Events

Cases of renal failure (including acute renal failure), some with fatal outcome, occurred in patients treated with everolimus. Renal function of patients should be monitored particularly where patients have additional risk factors that may further impair renal function.

Elevations of serum creatinine, usually mild, and proteinuria have been reported in patients taking everolimus. Monitoring of renal function, including measurement of blood urea nitrogen (BUN), urinary protein, or serum creatinine, is recommended prior to the start of everolimus therapy and periodically thereafter. Please refer to Table 4 for management of non-hematologic toxicities related to everolimus.

CONFIDENTIAL

STUDY DRUG(S): EVEROLIMUS
FINAL PROTOCOL DATE: 19 JUNE 2014

SCRI INNOVATIONS STUDY NUMBER: BRE 212
VERSION 1.0

6.2.6 Management of Stomatitis, Oral Mucositis and Mouth Ulcers

Adverse Drug Reaction	Severity	Everolimus Dose Adjustment and Management Recommendations
Stomatitis	Grade 1 (Minimal symptoms, normal diet)	No dose adjustment required. Manage with non-alcoholic or salt water (0.9%) mouth wash several times a day.
	Grade 2 (Symptomatic but can eat and swallow modified diet)	Temporary dose interruption until recovery to grade ≤ 1 . Re-initiate everolimus at the same dose. If stomatitis recurs at grade 2, interrupt dose until recovery to grade ≤ 1 . Re-initiate everolimus at a lower dose. Manage with topical analgesic mouth treatments (e.g. benzocaine, butyl aminobenzoate, tetracaine hydrochloride, menthol or phenol) with or without topical corticosteroids (i.e. triamcinolone oral paste)*.
	Grade 3 (Symptomatic and unable to adequately eat or hydrate orally)	Temporary dose interruption until recovery to grade ≤ 1 . Re-initiate everolimus at lower dose. Manage with topical analgesic mouth treatments (i.e. benzocaine, butyl aminobenzoate, tetracaine hydrochloride, menthol or phenol) with or without topical corticosteroids (i.e. triamcinolone oral paste)*
	Grade 4 (Symptoms associated with life-threatening consequences)	Discontinue everolimus and treat with appropriate medical therapy.

* using agents containing alcohol, hydrogen peroxide, iodine, and thyme derivatives in management of stomatitis is not recommended as they may worsen mouth ulcers.

Patients with a clinical history of stomatitis/mucositis/mouth ulcers and those with gastrointestinal morbidity associated with mouth/dental infections, irritation of esophageal mucosa (e.g. gastroesophageal reflux disease [GERD]) must be monitored even more closely. Patients should be instructed to report the first onset of buccal mucosa irritation/reddening to their study physician immediately.

Stomatitis/oral mucositis/mouth ulcers due to everolimus should be treated using local supportive care. Please note that investigators in earlier studies have described the oral toxicities associated with everolimus as mouth ulcers, rather than mucositis or stomatitis. If your examination reveals mouth ulcers rather than a more general inflammation of the mouth, please classify the AE as such. Please follow the paradigm below for treatment of stomatitis/oral mucositis/mouth ulcers:

1. For mild toxicity (Grade 1), use conservative measures such as non-alcoholic mouth wash or salt water (0.9%) mouth wash several times a day until resolution.
2. For more severe toxicity (Grade 2 in which case patients have pain but are able to maintain adequate oral alimentation, or Grade 3 in which case patients cannot maintain adequate oral alimentation), the suggested treatments are topical analgesic mouth

CONFIDENTIAL

STUDY DRUG(S): EVEROLIMUS
FINAL PROTOCOL DATE: 19 JUNE 2014

SCRI INNOVATIONS STUDY NUMBER: BRE 212
VERSION 1.0

treatments (i.e., local anesthetics such as, benzocaine, butyl aminobenzoate, tetracaine hydrochloride, menthol, or phenol) with or without topical corticosteroids, such as triamcinolone oral paste 0.1% (Kenalog in Orabase®).

3. Agents containing alcohol, hydrogen peroxide, iodine, and thyme derivatives may tend to worsen mouth ulcers. It is preferable to avoid these agents.
4. Antifungal agents should be avoided unless a fungal infection is diagnosed. In particular, systemic imidazole antifungal agents (ketoconazole, fluconazole, itraconazole, etc.) should be avoided in all patients due to their strong inhibition of everolimus metabolism, therefore leading to higher everolimus exposures. Therefore, topical antifungal agents are preferred if an infection is diagnosed.

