6. DOSE MODIFICATIONS

All toxicities will be graded utilizing the NCI CTCAE v 4.0 (<http://evs.nci.nih.gov/ftp1/CTCAE/CTCAE>). If toxicity occurs, the toxicity will be graded, and appropriate supportive care treatment will be administered to decrease the signs and symptoms thereof. Dose adjustments will be based on the organ system exhibiting the greatest degree of toxicity.

Adverse events most frequently observed with everolimus are rash, stomatitis/oral mucositis, non-infectious pneumonitis, fatigue, headache, anorexia, nausea, vomiting, diarrhea, and infections. Overall, the most frequently observed laboratory abnormalities include neutropenia, thrombocytopenia, hyperglycemia, hypercholesterolemia, and/or hypertriglyceridemia. The majority of these AEs have been of mild to moderate severity (NCI CTCAE Grade 1-2).

The dose level reductions for everolimus to be used in this study are shown in Table 1.

If everolimus is interrupted for any reason, and the patient has no toxicity related to anti-estrogen therapy, the patient should continue anti-estrogen therapy per schedule. If the patient discontinues everolimus for any reason, they should continue to receive anti-estrogen therapy if patient is deriving clinical benefit from the therapy.

Table 1 Everolimus Dose Level for Toxicity

Dose Level	Everolimus
Starting Dose	10 mg daily
Dose Level -1	5 mg daily
Dose Level -2	5 mg every other day

No more than 2 dose reductions for everolimus are permitted. Patients who need an additional dose reduction will be required to discontinue everolimus.

Table 2 lists the dosing guidelines for everolimus-related hematologic toxicities, Table 3 and Table 4 list the dosing guidelines for everolimus-related non-hematologic toxicities.

CONFIDENTIAL

STUDY DRUG(S): EVEROLIMUS
FINAL PROTOCOL DATE: 19 JUNE 2014

SCRI INNOVATIONS STUDY NUMBER: BRE 212
VERSION 1.0

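### For a first Grade 4 stomatitis, Protocol Table 4 restarts everolimus at a lower dose and Section 6.2.6 stops it, and the protocol does not say which rule applies

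*Protocol*

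**What the plan says.** Two parts of Protocol Section 6 set the everolimus dose after a Grade 4 oral event.

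- **Table 4 (Section 6.2), Grade 4 AE row.** Everolimus is held until the event improves to Grade 1 or less, or to baseline. Then: "Reintroduce everolimus at one dose level lower, if available". The row lists no exceptions.
- **Section 6.2.6, Grade 4 row of the stomatitis table.** "Discontinue everolimus and treat with appropriate medical therapy". No restart is offered. For Grades 2 and 3 the same table uses a temporary interruption followed by a restart, so discontinuation at Grade 4 means a permanent stop.

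Table 4's scope is stated twice. Section 6 says: "Table 3 and Table 4 list the dosing guidelines for everolimus-related non-hematologic toxicities". Section 6.2 says: "Dose reductions and management of non-hematologic toxicities related to everolimus are defined in Table 3 and Table 4".

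Two further rules limit the restart. Section 6 allows two reductions and adds: "Patients who need an additional dose reduction will be required to discontinue everolimus". The last row of Table 4 ("Any non-hematologic toxicity requiring interruption for" more than 28 days) also ends in discontinuation.

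**The concern.** Both instructions are current protocol text and both cover the same event. A site working from Table 4 would re-challenge a patient after a life-threatening toxicity. A site working from Section 6.2.6 would stop the drug. With about 9 sites, patients with the same event could be managed differently.

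There is a smaller reporting consequence. Safety and tolerability are the secondary objective, and the SAP's adverse event overview (Table 10) counts events leading to discontinuation, interruption and reduction on separate lines. The same clinical event could fall on different lines depending on which page the site followed.

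**Working it through.** No arithmetic applies, so the check sets the two rules side by side and then looks for a statement of precedence.

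**Step 1. Where the rules diverge.** The dose levels are those of Table 1 in Section 6. The event is a first Grade 4 stomatitis.

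| Dose at the event | Recovery | Table 4 with Section 6 | Section 6.2.6 | Same action? |
|---|---|---|---|---|
| 10 mg daily | 28 days or less | Restart at 5 mg daily | Discontinue | No |
| 5 mg daily | 28 days or less | Restart at 5 mg every other day | Discontinue | No |
| 5 mg every other day | 28 days or less | No lower level, so discontinue | Discontinue | Yes |
| Any | More than 28 days | Discontinue | Discontinue | Yes |

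A Grade 4 event that recurs after a dose reduction ends in discontinuation under both texts. The conflict is therefore confined to the first two rows.

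**Step 2. Whether the protocol says which rule wins.**

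- Sections 6 and 6.2 point to Table 4, and Table 4 itself names mucositis in two of its rows.
- Table 4's exceptions (pneumonitis, hyperglycemia, hypercholesterolemia) sit in the Grade 2 mucositis and Grade 3 row. Stomatitis is not among them.
- Sections 6.2.3 and 6.2.5 hand dosing back to Table 4: "Please refer to Table 4 for management of non-hematologic toxicities related to everolimus". Section 6.2.6 has no such referral, which suggests it was meant to stand alone.
- Precedence is written down elsewhere. The footnote to Table 3 gives it to the HCV flare guidance, and Section 6.2.9 tells sites to follow Table 5 for pneumonitis. Nothing equivalent covers the stomatitis dose table.
- The sentence in Section 6.2.6 telling sites to follow a paradigm introduces the numbered list on local care for Grades 1 to 3 and on antifungals. It does not address Grade 4 dosing.
- The general rule in Section 6 about the most affected organ system chooses between organ systems. It does not choose between two rules for one event.

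**Step 3. Grades 2 and 3.** Restart doses also differ in some cases.

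| Event | Table 4 | Section 6.2.6 |
|---|---|---|
| Grade 3, resolved within 7 days, no recurrence within 28 days, not a recurrence after dose reduction | Same dose | Lower dose |
| First intolerable Grade 2, more than 7 days to resolve | Lower dose | Same dose |
| Intolerable Grade 2 recurring after 28 days, no earlier reduction, resolved within 7 days | Same dose | Lower dose |

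The first line is literal. The other two assume that mucositis in Table 4 and stomatitis in Section 6.2.6 mean the same event. Neither text is the stricter one throughout, so an informal habit of using the safer text would not pick out one governing section.

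**The case against.** The strongest reply is that ordinary reading settles the matter. Section 6.2.6 is event-specific and graded, and its table is expressly about everolimus dose adjustment. Table 4's Grade 4 row is a catch-all. Where the protocol wants Table 4 to decide, as in Sections 6.2.3 and 6.2.5, it says so. Section 3.3 separately ends treatment for irreversible or intolerable toxicity, and even Table 4 restarts only after recovery and at a reduced dose. On this view all that is missing is a cross-reference.

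Most of this stands, and Section 6.2.6 is the likelier rule. It does not remove the contradiction: Table 4 is named twice as the dosing rule, mentions mucositis itself, and carries no exception here, although the protocol writes out precedence for other toxicities.

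Other objections limit what can be claimed:

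- **Scope.** A reader might infer that the conflict is equally explicit for oral mucositis and mouth ulcers. The dose table's row label is stomatitis only, and the section asks investigators to classify mouth ulcers as such. The extension rests on the section heading and the surrounding text, which treat the three together.
- **Pneumonitis.** The Grade 4 row omits this exception too, and a reader might count a second conflict. Section 6.2.9 already directs sites to Table 5, so precedence there is settled in substance.
- **Frequency.** A reader might turn the 8% stomatitis rate in Section 1.2 into an expected number of Grade 4 cases. That rate pools Grades 3 and 4, comes from another trial, and is given without a split.

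**Conclusion.** The inconsistency is real and narrow. It concerns a first Grade 4 stomatitis with a lower dose level available and recovery in 28 days or less, where Table 4 restarts everolimus and Section 6.2.6 stops it. Section 6.2.6 probably governs, but that is inferred from its specificity and not stated.

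The case for correction rests on the seriousness of the event and not on how often it will occur. The documents do not allow the number of Grade 4 cases to be estimated, and it may be zero. A reader might also infer that the efficacy result is at stake. The documents do not support that: no endpoint definition, sample size or PFS analysis method depends on which rule is chosen.

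The conclusion assumes that discontinuation in Section 6.2.6 is permanent, as the contrast with its Grade 2 and 3 rows indicates. Covering oral mucositis and mouth ulcers further assumes that the heading sets the scope of the dose table.

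**What to change.** In Table 4's Grade 4 AE row, add: *except stomatitis, oral mucositis and mouth ulcers: discontinue everolimus at the first Grade 4 event (Section 6.2.6)*. For consistency, the same clause can point Grade 4 pneumonitis to Table 5.

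For Grades 2 and 3, the sponsor should state which text sets the restart dose. A blanket rule that the lower dose applies is not recommended. It would be a new clinical rule, and at 5 mg every other day it would force a stop where one of the current texts allows a restart at the same dose.

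Leave Table 4's recurrence rows in force, including "If toxicity recurs at Grade 3, consider discontinuation", together with the rule on interruptions longer than 28 days.

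The cost is a protocol clarification and a site memo. At most a few patients would be stopped instead of re-challenged. Sample size and planned analyses do not change.
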